Nutrition diary	X ^m	X ^m	X ^m	X ^m	X ^m	X ^m	X ^m	X ^m	X ^m	X ^m	X ^m	X ^m	X ^m	X ^m	X ^m	X ^m	X ^m		
Exploratory Assessments																			
CFC and associated labs ⁿ			X ⁿ												X ⁿ				
Capillary ketones ^o	X		X ^o	X ^d		X ^d		X ^d		X ^d		X ^d		X ^o				X	
CGM ^p	X ^p	X ^p	X ^p	X ^p	X ^p	X ^p	X ^p	X ^p	X ^p	X ^p	X ^p	X ^p	X ^p	X ^p	X ^p	X ^p	X ^p		
Urine Glc ^q			X	X ^d	X	X ^d	X	X ^d	X	X ^d	X	X ^d	X	X	X	X	X		
AGL variant analysis	X																		
WBC, RBC, Serum & Plasma for Future Use ^q				X ^d	X		X							X		X		X	

Footnotes continue on the following page.

^a The ISV includes a review of the subject's diet. Within the first 2 weeks after the ISV, the Investigator will review nutrition diary data to determine if nutrition optimization is needed. If nutrition optimization is not needed, the STV occurs in clinic approximately 2 weeks after the ISV, and the Baseline/Week 0 Visit occurs approximately 6 weeks after the STV. If nutrition changes are needed, a 2- to 4-week period of nutrition optimization will be performed. The first

NOV occurs as a phone visit approximately 2 weeks after the ISV; during nutrition optimization, NOVs can occur weekly or more frequently as needed. When the Investigator determines that the subject has achieved nutritional optimization the STV is performed. [Figure 3](#) provides a schematic of screening for DB-RD cohorts.

^b In the event a subject has an ET, all efforts will be made to monitor the subject through the end of the study. At minimum, a safety follow-up phone call will occur within the 4 weeks following the subject's last treatment.

^c Complete physical exam is required at ISV, BL/W0, W2, and EOS III W48/ET. Targeted physical exams may be performed at STV, W4, W6, W8, and W10.

^d Assessments to be performed prior to dosing on the same day as dosing visits or on the day before dosing for visits that include a CFC (ie, W10). When applicable, the following assessments can be collected within a week prior to dosing: HHD, PROMIS questionnaires, SF-36v2, and GNEM-FAS expanded version.

^e Refer to [Table 7](#) for the timing of vital sign assessments during dosing.

^f Refer to [Table 8](#) for details of PK sampling. Please note that sample collections are marked for W1, W2, W9, W10, and W12 in this table ([Table 6](#)) corresponding to a sample collection 7, 14, and 28 days after infusion of UX053 on W0 and/or W8 as outlined in the final rows of the first column in [Table 8](#); a 28-day post infusion collection is only collected for the W8 assessment for DB-RD cohorts. PK samples are also collected 24-hours post infusion as noted in [Table 8](#).

^g Sample to be collected pre-dose and at the end of the infusion. Post-infusion blood samples should be collected in the opposite arm of the infusion to avoid dilution.

^h Optional safety assessments to be performed (and repeated as necessary) at the discretion of the Investigator if nutrition changes are made during screening.

ⁱ Close monitoring is required for subjects who develop elevations in ALT > 3x ULN and > 2x their baseline value, or elevation in ALT > 3x ULN with INR > 1.5. This includes repeating liver enzymes and INR within 48 hours and consideration of additional diagnostic tests such as liver ultrasound ([Section 10.1.5](#)).

^j All efforts should be made for urine collections to be consistently taken from the first morning void.

^k All imaging assessments (liver MRI, liver MRS, and Fibroscan or ultrasound elastography) can be conducted at any time during screening or within 1 week prior to the corresponding visit. Liver MRS are only required at sites with capability. Scanning for liver MRS can be conducted immediately following the liver MRI. If feasible, glycoNOE imaging of the liver, may be collected at the time of the liver MRI.

^l A 3- to 4-hour fasting period is preferred, but not required, prior to blood collection for serum HDL and LDL. All efforts should be made to obtain samples for HDL and LDL consistently for a given subject.

^m Nutrition diary recordings should be recorded at least 3 consecutive days per week through Screening and for the 3 consecutive days in the week leading up to each subsequent visit. Qualified Investigator site staff should review nutrition diary data at each visit.

ⁿ CFC is an optional assessment. Please see [Section 10.5.1](#) for a description of the CFC. Cortisol must be measured between 6 and 9 am on the morning of the CFC. The CFC begins after completion of a meal (breakfast for daytime fast or dinner for overnight fast) or associated cornstarch consumption (as applicable). A venous blood sample for measurement of glucose, cortisol, glucagon, insulin, C-peptide, and β -hydroxybutyrate will be collected at the beginning (ie, immediately after completion of the meal or the evening cornstarch, as applicable), at end of the CFC, and 30 minutes after the end of the CFC. During the CFC, venous blood samples for STAT analysis of glucose will be collected through an indwelling catheter every 60 minutes (\pm 5 minutes) until the glucose level decreases to \leq 70 mg/dL (\leq 3.9 mmol/L). Thereafter, venous blood glucose is measured approximately every 30 minutes (\pm 5 minutes) until the end of the CFC. The CFC will end when the subject's glucose level decreases to $<$ 54 mg/dL ($<$ 3.0 mmol/L), when the subject experiences signs and symptoms of hypoglycemia, or the fast reaches 12 hours (daytime fast) or 15 hours (overnight fast) without hypoglycemia, whichever occurs first.

^o Assessment for capillary ketones does not need to be repeated for visits that include the CFC (ie, W10 Visit).

^p The subject will receive a CGM and HHG device and will be trained on proper use at the ISV. The CGM is intended to be worn continuously from ISV to the W24 Visit. The CGM will be worn again for the week prior to the W36 and EOS III W48/ET Visits. If the CGM device alarm notifies a subject that their blood sugar is abnormally high or low or the subject suspects their blood sugar is abnormally high or low, the subject will need to check their blood sugar

with a HHG that will be provided by Ultragenyx at ISV. When CGM data is being collected, all subjects will connect their CGM and HHG devices to a study-provided laptop weekly and upload CGM and HHG data. At remote visits, in conjunction with assessments performed by a home health nurse, the site will contact subjects by telephone or videoconference to confirm the CGM device is properly in use and data was uploaded; answer any questions regarding or help troubleshoot (if necessary) CGM device use; and review CGM data, HHG data (when applicable), and nutrition diary entries; outside of scheduled visits, these telephone calls will occur as needed. At in-clinic visits, a conversation between the site and the subject should occur to ensure CGM compliance and troubleshoot if needed.

^q RBC, WBC, serum and plasma samples will be collected for future biomarker assessments yet to be determined.

Note: White columns indicate in-clinic visits (ISV, STV, BL/W0, W2, W4, W6, W8, W10, and EOS III W48/ET). Gray columns indicate visits conducted at home (NOV, W1, W3, W5, W7, W9, W12, W24, and W36). A telephone call is required if NOVs occur, but not for W1 and W9. A visit from a home health nurse is required for W1, W3, W5, W7, W9, W12, W24, and W36, but may not be necessary for NOVs.

Note: Laboratory assessments included in chemistry, hematology, and urinalysis are provided in [Appendix 3](#).

AGL, amylo- α -1,6-glucosidase 4-alpha-glucanotransferase; AH50, alternative complement activity; ALT, alanine aminotransferase; BL, baseline; BNP, B-Type Natriuretic Peptide; CFC, controlled fasting challenge; CGM, continuous glucose monitor; CH50, classical pathway complement activity; CK, creatinine kinase; CK-M/B, CK-muscle/brain; COVID-19, coronavirus disease 2019; CRP, C-reactive protein; DB, double-blind; ECG, electrocardiogram; EOS, end of study; ET, early termination; Glc₄, glucose tetrasaccharide; glycoNOE, glycogen nuclear overhauser enhancement; GNEM-FAS, GNE Myopathy Functional Activities Scale; GSD, glycogen storage disease; HDL, high density lipoprotein; HHD, handheld dynamometry; HHG, handheld glucometer; IL-6, interleukin-6; ISV, Initial Screening Visit; LDL, low density lipoprotein; MRI, magnetic resonance imaging; MRS, magnetic resonance spectroscopy; NOV, Nutrition Optimization Visit; PROMIS, Patient-Reported Outcomes Measurement Information System; PK, pharmacokinetic; PT/INR, prothrombin time/international normalized ratio; RBC, red blood cell; RD, repeat dose; sC5b-9, soluble Complement 5b-9; SF-36v2, Short Form Health Survey 36 Version 2; STV, Stabilization Visit; ULN, upper limit of normal; W, Week; WBC, white blood cell.

Table 7: Schedule of Vital Sign Assessments at Infusion Visits

Pre-Infusion	
Within 30 min prior to initiating the infusion	X
After initiation of infusion^a	
15 min (\pm 5 min)	X
30 min (\pm 5 min)	X
45 min (\pm 5 min)	X
1 hr (\pm 10 min)	X
2 hr (\pm 10 min)	X
3 hr (\pm 10 min)	X
4 hr (\pm 10 min)	X
5 hr (\pm 5 min)	X
6 hr (\pm 5 min)	X
7 hr (\pm 10 min)	X
8 hr (\pm 10 min)	X
9 hr (\pm 10 min)	X
10 hr (\pm 10 min)	X
16 hr (+/- 1hr)	X
24 hr (+/- 2hr)	X
Discharge ^b	X

^a All post-infusion time points refer to time from the beginning of the infusion.

^b The discharge vital signs assessment is not required and can be used to record any vital signs taken just prior to discharge.

Note: This schedule applies to every infusion of study drug, regardless of cohort (SAD, DB-RD, or OL-RD)
 hr, hour; min, minute; OL, open-label; DB-RD, randomized, double-blind, placebo-controlled; RD, Repeat Dose;
 SAD, Single Ascending Dose.

Table 8: Schedule of PK Assessments during and following Study Drug Infusion

Study Cohort	SAD Cohorts		RD Cohorts			
Sample Type	Blood	Plasma	Blood	Plasma	Blood	Plasma
Analyte	AGL mRNA	ATX95	AGL mRNA	ATX95	AGL mRNA	ATX95
Infusion	Day 0 Infusion		DB-RD and OL-RD Week 0 Infusion		DB-RD Week 8 Infusion &OL-RD Week 12 Infusion	
Pre-infusion						
Within 1 hr prior to initiating infusion	X	X	X	X	X	X
After initiation of infusion						
1 hr (\pm 10 min) ^a	X	X	X	X	X	X
3 hr (\pm 10 min)	X	X	X	X	X	X
4 hr (\pm 10 min) ^b	X	X	X	X	X	X
4.5 hr (\pm 10 min)	X	X	X	X	X	X
5 hr (\pm 10 min)	X	X	X	X	X	X
6 hr (\pm 20 min)	X	X	X	X	X	X
8 hr (\pm 30 min)	X	X	X	X	X	X
10 hr (\pm 30 min)	X	X	X	X	X	X
24 hr (\pm 2 hr); Day 1	X	X	X	X	X	X
96 hr (\pm 24 hr); Day 4	X	X				
168 hr (\pm 24 hr); Day 7	X	X	X	X	X	X
336 hr (\pm 48 hr); Day 14	X	X	X ^c	X ^c	X	X
504 hr (\pm 48 hr); Day 21	X	X				
672 hr (\pm 48 hr); Day 28	X	X	X ^d	X ^d	X	X

^a The 1-hour sample during infusion is to be collected prior to the infusion rate change (refer to Pharmacy Manual for additional details regarding the infusion rate).

^b The 4-hour sample is to be collected at the end of the infusion.

^c Subjects in the DB-RD cohorts receive study drug at the (Week 2) Day 14 Visit, and therefore, their sample is to be collected predosing. While subjects in the OL-RD cohorts do not receive study drug at the Week 2 (Day 14) Visit, their sample should still be collected within the specified time window.

^d Sample is to be collected pre-dosing at the Week 4 (Day 28) Visit for the OL-RD cohorts only.

Note: 0 hr is the start of the drug infusion.

Note: If the total infusion time is extended beyond 4 hours, a blood sample should be collected at the new EOI time. If the new EOI time overlaps with a prespecified time point, sampling should continue at the next scheduled time point.

AGL, amylo- α -1,6-glucosidase 4-alpha-glucanotransferase; EOI, end of infusion; hr, hour; min, minute; PK, pharmacokinetic; DB, Randomized Double-Blind Placebo-Controlled; RD, Repeat Dose; OL, Open-Label; SAD, Single Ascending Dose.

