8. Females of childbearing potential must have a negative pregnancy test at screening (and rescreening, as applicable) and be willing to have additional pregnancy tests during the study. Subjects of child-bearing potential or males who are sexually active with partners of child-bearing potential must consent to use a highly effective contraceptive method, as described in [Appendix 4](#), from the Period following the signing of the informed consent through 30 days after last dose of study drug
9. For subjects rescreening into OL-RD cohorts after treatment with UX053 in a SAD cohort, subjects must meet the following criteria:
 - a. If a significant rise in ALT occurs after the prior dose, ALT should show a decreasing trend toward the subject's baseline value
 - b. Total bilirubin is within normal limits
 - c. Platelets are within normal limits
 - d. International normalized ratio (INR) is within normal limits

Each subject must not meet the exclusion criteria listed below at screening (ISV for DB-RD cohorts) and baseline (Day 0 for SAD cohorts or Week 0 in all RD cohorts), as applicable, to be enrolled in the study:

1. History of liver transplant, including hepatocyte cell therapy/transplant, or active listing for liver transplant
2. History of cirrhosis, or presence of any of the following:
 - a. Total bilirubin ≥ 1.3 mg/dL and INR ≥ 1.3
 - b. Evidence of portal hypertension, including, but not limited to the following symptoms splenomegaly, ascites, thrombocytopenia, esophageal varices, or history of hepatic encephalopathy

- c. Model for End Stage Liver Disease (MELD) score > 12
- 3. Current Hepatitis B or C infection or history of chronic Hepatitis B or C infection
- 4. Severe renal impairment defined as a glomerular filtration rate (GFR) \leq 29 mL/min ([Levey et al., 2005](#)).
- 5. Any prior history of hepatocellular carcinoma or presence of liver adenoma $>$ 5 cm at the longest diameter or $>$ 3 cm and \leq 5 cm in size that has an annual growth rate of \geq 0.5 cm per year
- 6. Current or history of malignancies in the 3 years prior to the Screening Visit (ISV for RD)
- 7. Hospitalizations related to GSD III disease between the Screening (ISV for RD) and Baseline Visit
- 8. Known history of human immunodeficiency virus infection

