- 9. Presence or history of any hypersensitivity reactions requiring medical evaluation and management (including injection/IRRs, such as lymphadenopathy) to UX053, its excipients, or any drug products that contain polysorbate or polyethyleneglycol (PEG). This may include vaccines that contain PEG or polysorbate
- 10. Significant cardiac disease, including heart failure with New York Heart Association (NYHA) Function Capacity III or IV or Objective Assessment C or D, unstable angina, or ejection fraction (EF) $<$ 35%, or uncontrolled arrhythmia or resistant hypertension ([Carey et al., 2018](#)). Mild cardiomyopathy and left ventricular hypertrophy (LVH) are allowed
- 11. Presence or history of any co-morbid condition or abnormal labs that, in the view of the Investigator, places the subject's safety at risk; places the subject at high risk of poor treatment compliance or not completing the study; or would significantly affect the interpretation of study results
- 12. Poorly controlled diabetes, defined as the presence of any of the following:
 - a. Hemoglobin A1C $>$ 8% ([Qaseem et al., 2018](#))
 - b. History of diabetic nephropathy, neuropathy, or retinopathy
 - c. History of diabetic ketoacidosis during the past year
- 13. Poorly controlled hypothyroidism, based on the judgement of the Investigator or Ultragenyx, whichever is most conservative
- 14. History of chronic coagulopathy, thrombophilia, or disorder of complement activation
- 15. Use of concomitant medications that alter prothrombin time/international normalized ratio (PT/INR), including warfarin and direct oral anticoagulants (eg, rivaroxaban, apixaban, and edoxaban). Patients who receive medications that affect platelet function, such as aspirin or clopidogrel, are allowed unless they have comorbidities that in the judgment of the Investigator place them at undue risk to participate in the study.

16. Current treatment with long-term immunosuppressive medications. This includes subjects with autoimmune conditions managed with immunosuppressive medications and solid organ transplant recipients.
17. Active tuberculosis requiring treatment in the past 3 years
18. Symptomatic coronavirus disease 2019 (COVID-19) infection
19. History of active alcohol and/or drug abuse that in the Investigator's assessment would impair the subject's ability to comply with the protocol

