8.3.2. Subject-level Redosing and Stopping Criteria

At any time after the first dose of study drug, if a marked increase in transaminases (ie, $> 2x$ the subject's baseline value and $3x$ ULN) is observed, liver enzymes, bilirubin, and INR should be obtained again within 48 to 72 hours. Study drug should not be re-administered unless the following criteria are met:

- If a significant rise in ALT occurs after the prior dose, ALT should show a decreasing trend toward the subject's baseline value
- Total bilirubin is within normal limits
- Platelets are within normal limits
- INR is within normal limits

Additionally, subjects who meet any of the following criteria will not be redosed:

- Subjects who develop new or worsening symptoms of liver disease (including new or worsening hepatomegaly) along with any increase in transaminase levels
- Subjects who require any blood product administration (eg, packed red blood cells, platelet, fresh frozen plasma) for management of consumptive coagulopathy

- Subjects who develop an ALT level that is $\geq 8x$ ULN and $> 2x$ the subject's baseline value in the absence of an alternative explanation

If a subject develops an IRR that meets diagnostic criteria for anaphylaxis ([Table 11](#)), epinephrine should be administered as initial rescue medication. For all other hypersensitivity reactions \geq Grade 2 in severity suspected to be due to immune activation, dexamethasone should be the initial rescue medication. The Medical Monitor must be notified if any rescue medication is used.

If dexamethasone (or equivalent) is used as a rescue medication, premedication with dexamethasone (or equivalent) should be considered for that subject's subsequent infusions after discussion with the Medical Monitor.

In the event of an IRR, action outlined in [Table 10](#) should be implemented based on the level of severity. Ultragenyx will confer with the DMC whenever subject- or study-level stopping criteria are potentially met.

Table 10: Action in the Event of an Infusion-Related Reaction

IRR CTCAE Severity	Action
Grade 1 (Mild)	The infusion may be slowed or interrupted temporarily and resumed at the original speed

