9.4. Prior and Concomitant Therapy

Subjects may receive concomitant medications as required, with the exception of those identified in Section 9.6 as prohibited.

The study site should indicate to laboratories if the subject is using any high dose biotin supplements (found in multivitamins, biotin supplements, and some supplements to promote hair, skin, and nail growth) to potential risk of assay interference (eg, troponin) (Section 10.1.5) (FDA, 2019a).

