9.6. Restricted or Prohibited Medications, Devices, and Procedures

The following are specifically prohibited during study participation, as noted in the exclusion criteria (Section 8.2):

- Use of any IP or investigational medical device within 30 days or for IP within 5 half-lives, whichever is longer, prior to screening (or rescreening, as applicable), or requirement for any investigational agent prior to completion of all scheduled study assessments
- Planned surgery, including dental surgeries, during the study

If a subject is on a drug that is metabolized primarily by cytochrome P450 2B6 (CYP2B6), caution is advised as UX053 may result in decreased CYP2B6 activity and altered exposure of the drug. Additional details regarding this potential interaction and nonclinical studies with UX053 are available in the IB.

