10.1.7. Pregnancy Testing

Female subjects of childbearing potential will have urine pregnancy tests at visits indicated in [Table 4](#), [Table 5](#), and [Table 6](#). For visits in which subjects are receiving study drug, results of

urine pregnancy testing should be reviewed prior to dosing. Females not of childbearing potential are not required to undergo pregnancy testing. Refer to [Appendix 4](#) for contraception guidance.

Female subjects with a positive pregnancy test at the Screening Visit (ISV for DB-RD) will not be enrolled in the study.

Additional pregnancy tests will be performed at any visit in which pregnancy is in question. A serum pregnancy test will be performed in the event of a positive or equivocal urine pregnancy test result or can be performed if pregnancy test by urine is not feasible.

Refer to [Appendix 2](#) for pregnancy reporting requirements.

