10.4.1.4. Prothrombin Time/International Normalized Ratio

Blood will be collected for the measurement of prothrombin time (PT) and to calculate PT/INR to aid in the assessment of liver health at time points specified in [Table 4](#), [Table 5](#), and [Table 6](#). For visits in which subjects are receiving study drug, laboratory samples will be collected prior to dosing. Samples will be processed by a central lab to ensure consistency across study sites.

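### PT/INR-altering medicines are barred only at entry: a repeat-dose subject who starts an anticoagulant after Week 0 may still be infused, without a deviation, if the laboratory redosing criteria are met

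*Protocol*

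**What the plan says.** **Entry.** Exclusion 15 (Synopsis, repeated in Protocol 8.2) is "Use of concomitant medications that alter prothrombin time/international normalized ratio (PT/INR), including warfarin and direct oral anticoagulants". Antiplatelet drugs such as aspirin or clopidogrel stay allowed unless the Investigator sees undue risk. The lead-in fixes the timing: "Each subject must not meet the exclusion criteria listed below at screening (ISV for DB-RD cohorts) and baseline", where baseline is Day 0 in SAD cohorts and Week 0 in RD cohorts. For entry to the open-label RD (OL-RD) cohorts, inclusion 9d adds a laboratory condition: "International normalized ratio (INR) is within normal limits".

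**During the study.** Protocol 9.4 states: "Subjects may receive concomitant medications as required, with the exception of those identified in Section 9.6 as prohibited". Section 9.6 presents its list as exclusion criteria that continue during participation. It has two items, investigational products or devices and planned surgery, followed by a caution on CYP2B6 substrates. PT/INR-altering medicines do not appear.

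**Redosing.** Protocol 8.3.2 opens with what to do after a marked transaminase increase and continues: "Study drug should not be re-administered unless the following criteria are met". The criteria are an ALT trend back towards baseline after a significant rise, and total bilirubin, platelets and INR within normal limits. It also bars redosing permanently after certain liver events, blood products for coagulopathy, or a Grade 3 or higher infusion reaction. No criterion refers to a medicine.

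**The concern.** Consumptive coagulopathy is one of three potential risks of UX053 named in Protocol 5.4.1, and prolonged PT/INR is one of its stated signs. The amendment history gives the reasons for exclusion 15 as subject safety and interpretation of liver-injury signals. Neither reason ends at Week 0. In RD cohorts most of the exposure comes later, as four further infusions in the double-blind (DB-RD) cohorts and three in OL-RD.

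At stake is mainly bleeding safety: study drug with a coagulopathy risk could be infused while an anticoagulant is in use. A secondary effect is that later INR values become harder to read. That effect is partial, because fibrinogen, d-dimer and platelets are also measured.

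**Working it through.** No figure in the plan needs reproducing. The check is a cross-reading, followed by simple counts.

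**Trace for an RD subject who starts a direct oral anticoagulant after Week 0**

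1. *Exclusion 15:* last assessed at Week 0. Its text has no words that extend it. Exclusions 21, 22 and 24 do extend themselves, to the whole study or to completion of assessments.
2. *Section 9.6:* the medicine is not listed.
3. *Section 9.4:* what 9.6 does not list is allowed.
4. *Section 8.3.2:* if ALT trend, bilirubin, platelets and INR all pass and no permanent bar applies, redosing is allowed.
5. *Appendix 5:* a deviation is noncompliance with the protocol. None has occurred.
6. *Section 10.1.8 and SAP 7.6:* the medicine is recorded and summarised. Neither section attaches any action to it.

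**Is the INR condition a substitute for the drug rule?** OL-RD entry requires both a normal INR (inclusion 9d) and no PT/INR-altering medicine (exclusion 15). So the protocol does not treat one as replacing the other at entry. After Week 0 only the laboratory condition remains.

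**Does it apply at every redose?** The criteria in 8.3.2 follow a sentence triggered by transaminases above 2x baseline and 3x ULN. They can be read as general or as applying only after such a rise. On the narrow reading, INR would not gate an ordinary redose at all. The text does not settle this.

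**Planned UX053 infusions after Week 0**

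- DB-RD: 3 cohorts x 3 active subjects = 9; 9 x 4 infusions (Weeks 2, 4, 6, 8) = 36
- OL-RD: up to 6 subjects (the planned SAD minimum) x 3 infusions (Weeks 4, 8, 12) = 18
- Total: 36 + 18 = 54 at most

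**Most that one affected subject could lose under the fix**

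- DB-RD: 4 of 5 doses. Within a cohort of 3 active subjects, 4 / (3 x 5) = 4/15 = 27% of active infusions.
- OL-RD: 3 of 4 doses.

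**End of the proposed window**

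- DB-RD: last dose at Week 8 + 4 weeks = Week 12
- OL-RD: last dose at Week 12 + 4 weeks = Week 16

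**The case against.** The strongest defence is that gating on the laboratory effect is a reasonable design. Exclusion 15 defines the class by its effect on PT/INR, and 8.3.2 tests INR. Nothing in the documents says that a subject on such a medicine keeps an in-range INR, or how often. Some likely reasons for anticoagulation are already excluded (thrombophilia, unstable angina, uncontrolled arrhythmia, planned surgery). Adverse events and medicines are reviewed at every RD visit. A Grade 3 or higher cardiopulmonary or neurological event pauses dosing whatever its cause. The Investigator, sponsor and DMC can each act on an individual's dosing (8.3.1, 8.3.3, 9.1.5).

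Much of this stands, and it limits the size of the point. It does not close the gap. The powers are discretionary, the screening is partial, and the in-range INR is stated here only as a condition.

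Three stronger readings are tempting but not supported:

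- *A reader might infer that INR alone gates redosing.* It does not. ALT trend, bilirubin and platelets are also required. INR is only the one criterion aimed at an anticoagulant's effect.
- *A reader might infer that central-laboratory timing defeats the INR condition.* Section 10.4.1.4 says "laboratory samples will be collected prior to dosing. Samples will be processed by a central lab to ensure consistency across study sites" and sets no deadline for the result, whereas 10.1.7 says results of "urine pregnancy testing should be reviewed prior to dosing". But a rule against redosing unless INR is normal presupposes a known result. Any delay would also affect every subject, on an anticoagulant or not. It is a separate question.
- *A reader might infer that the three-subject INR count in 8.3.3 would be seriously distorted.* One subject cannot reach three, and a false count leads to a pause, which is the cautious direction.

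**Conclusion.** The gap is real and rests on the text alone. In the RD cohorts a PT/INR-altering medicine started after Week 0 is permitted, and infusion may continue without a deviation when the laboratory criteria pass. A cheap improvement is warranted, mainly for bleeding safety at repeat infusions.

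Its size cannot be expressed as a rate. A reader might take the 54 infusions as the number at risk. They are all the planned active infusions after Week 0, and only those in a subject who starts such a medicine are at issue. The documents give no basis for estimating how many that would be.

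Nor should a reader infer that reported results are compromised. SAP 8 states that the study ended after 4 subjects in Cohort 1S and 4 in Cohort 2S, with SAD analyses only, and SAD subjects receive one dose. The point concerns the RD cohorts as written and any reuse of the protocol.

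**What to change.** Add the exclusion 15 drug classes to the 9.6 prohibited list, from first dose through 28 days after the last dose, and keep the antiplatelet allowance. Add one sentence: if such a medicine is clinically needed, give it, withhold further study drug while it is in use, decide resumption with the Medical Monitor, and continue follow-up under 8.3.1.

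The 28 days are a proposal. They do not come from Table 14 in Appendix 2, whose collection period runs to the later of 28 days after the last dose or the final study visit.

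**Cost.** One bullet and one sentence. No new data are needed, since 10.1.8 already records medicines and their dates. The downside is the dose loss shown above, and under 8.3.4 a dosed subject is not replaced. A short course would cost fewer doses, because resumption is possible.

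**What it leaves open.** It does not remove drug-raised INR values from the 8.3.3 three-subject count, and it does not settle when the central-laboratory INR must be available. Whether the 8.3.2 criteria apply to every redose would also need its own clarification.
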